2.6. Implementation outcomes

The study will employ three measures for the assessment of protocol adherence and quality control: (i) competency of facilitators, (ii) fidelity to the intervention protocol, (iii) attendance by adolescents and caregivers. First, the competency of facilitators of EASE and TeamUp will be assessed using the Working with Children Assessment of Competencies Tool (WeACT) (13-items and 8-items, respectively) (Jordans et al., 2021) and facilitators of BeThere will be assessed using the 15-item Enhancing Assessment of Common Therapeutic factors (ENACT) instruments (Kohrt et al., 2015). The WeACT and ENACT instruments aim to assess common factors in psychological treatments, including task-sharing initiatives with non-specialists across diverse cultural settings. The WeACT is used to assess competencies for working with children and

adolescents, whereas the ENACT assesses competencies for working with adults (in this study, the caregivers of enrolled adolescents). Competencies of facilitators will be assessed using insession observation of every facilitator by coaches/supervisors once per 2 months. . The WeACT and ENACT have already been translated and adapted for use in Uganda. Second, the fidelity to intervention protocol will be assessed using self-developed instruments designed to assess the implementation of TeamUp, EASE and BeThere. Intervention fidelity is assessed by facilitators themselves for all sessions and through observations of every facilitator by team-leader/project officer once per week . Third, attendance of TeamUp, EASE and BeThere intervention sessions by children and caregivers will be monitored using attendance logs (EASE and BeThere) and digital attendance app or attendance logs (TeamUp). Collected data on these implementation indicators (competence, fidelity and attendance) will routinely be made available to all supervisors/mentors for TeamUp, EASE and BeThere. This will allow for data-driven supervision and mentoring, wherein all supervisors/mentors will be trained to access the data and techniques and strategies to apply if the data on any of these indicators shows that implementation is inadequate (i.e. competence rating that indicate potentially harmful behavior [e.g. level 1 on ENACT items]; fidelity and attendance scores that indicate low levels [e.g. below 70%]). See Table 3 for an overview.

Table 3: Overview of assessment of Quality-of-Care indicators

	Competence		Fidelity		Attendance	
	What?	How?	What?	How?	What?	How?
BeThere	ENACT (+ selected GroupACT)	8 items + x g-ACT In session observation of every facilitator by coaches at once per 2 months	BeThere Fidelity tool	8 items Self report every session In session observation of every facilitator by teamleader/ PO at once per week	Paper and pencil	Every session, completed by facilitator
EASE	WeACT (+ selected GroupACT)	13 items + x g-ACT In session observation of every facilitator by coaches at once per 2 months	EASE Fidelity tool	10 items Self report every session In session observation of every facilitator by teamleader/ PO at once per week	Paper and pencil	Every session, completed by facilitator
TeamUp	WeACT (+ selected GroupACT)	8 items + x g-ACT In session observation of every facilitator by coaches at once per 2 months	TeamUp Fidelity tool	24 items Self report every session In session observation of every facilitator by teamleader/ PO at once per week	Attendance app or Paper and pencil	Every session, completed by facilitator

2.7. Monitoring

In addition, we will (i) track the number of cases detected and referred by gatekeepers using the ReachNow tool, (ii) track the number of referrals made to case management of specialized mental

health services, (iii) track the number of schools personnel that participated in the Community Tales workshops. Furthermore, before and after assessments will be done for each of the TeamUp, BeThere and EASE intervention groups on 25% of the participants (randomly selected), using the some of the same instruments that are also used in the cRCT (Instruments section above). See Table 4 below for an overview. In addition we will interview n=2 intervention participants per cohort/term to elicit Stories of Change and n=5 intervention participants for Community Feedback and Response Mechanism interviews (which is standard monitoring and evaluation practice within War Child).

Table 4: Overview of outcome monitoring

Intervention	When	Instrument	Construct	Extra	
BeThere	Before and after each intervention group (25%)	BPQ Kessler-10	Parenting	Stories of Change with n=2 per intervention per cohort CFRM with random n=5 per intervention per months	
EASE		ММАРР	Psychological distress		
TeamUp		Stirling Wellbeing Scale	Psychosocial wellbeing		

2.7.1. Instrument preparation

Instruments will be administered in Kinyabwisha, Congolese Kiswahili, Runyankole, Runyoro/Rutooro, which are the most spoken languages in the study sample. Prior to the current study we went through a rigorous process of translation, adaptation and validation of the abovementioned instruments for the above-mentioned languages and for use within the context and sample of the current study, specifically for the current study. This work has already been IRB approved (MAKSHSREC [29/08/24]), hence details are not included in this protocol. In brief, the process included; (i) translation by bilingual translator; (ii) review and back-translation by a bilingual mental health professional; (iii) cognitive interviewing (n=108 children; n=24 caregiver – across different instruments and languages); (iv) Focus Group Discussions (n=180 children; n=40 caregivers – across different instruments and languages); (v) harmonization and final adaptations by investigator team; (vi) final back-translation by different bi-lingual expert as step #2; (vii) psychometric testing (n=400 children; n=200 caregivers – across different instruments and languages).

2.7.2. Costs analyses instruments

Cost-analyses tool [RQ2] In order to perform an exploratory economic evaluation of the care system, the following instruments will be used: (i) a cost template form where we request information about resource inputs that go into the delivery, training and supervision the intervention(s) and their unit costs; (ii) resource use questionnaires for adolescents and caregivers, to assess in-patient and outpatient service use and costs, whereby caregivers will report for themselves and the index adolescent participant, and adolescent participants will report for themselves; this will be completed at all follow-up assessments (T1-T2). Costs of the different intervention components will be combined with information from the implementing team about the intensity of the interventions that were delivered during the study. Information sources that we will draw from include project administration data such as manuals, attendance and budget sheets.

The cost template form includes 71 items categorized into 12 domains covering information about staff or volunteer hours required for the delivery of the intervention, training and supervision, as well as other resource inputs such as costs linked to venue hire, traveling, material and equipment. The adolescent/caregiver resource use questionnaires to assess service use will be adapted from the Client Service Receipt inventory developed by Beecham and Knapp (2001); https://www.pssru.ac.uk/csri/international-versions/). The caregiver version of the questionnaire consists of two parts (a, b): part a includes 7 questions about caregivers past use of physical and mental health services and wider support and advice (e.g., with debt, career), as well as changes in ways they save and spend money (including for their children's education). Part b) asks 8 questions about their children's use of physical and mental health services and support and advice, as well as about school attendance, and changes in ways they save or spend money. In the version for adolescents, adolescents are asked the same 8 questions.

2.8. Cluster randomization and participant selection

2.8.1. Randomization of clusters

For research question 1 [RQ1], we will follow a two-stage sampling process. The first stage involves stratified randomization of the 18 clusters. Clusters (i.e. zones) are selected based on the following eligibility criteria: (i) Presence of DRC refugees (target is majority >70% in overall sample); (ii) Operational capacity for War Child Alliance or partner; (iii) No War Child Alliance evidence-based mental health interventions (i.e. TU, BeThere, EASE) or comparable interventions by other organizations implemented in the 6 months prior to baseline; (iv) OPM

Approval or District authorities approvals. The cRCT will randomize 18 clusters to experimental or control arm, using a covariate-constrained or stratified randomization to achieve baseline balance. Within each of the 18 clusters, 1 school is selected following criteria (*Note*: most Zones only have one school that matches these criteria): (i) Willingness and permission to participate; (ii) sufficient pupils between 11-16 (n > 300); (iii) Pupil lists or registers are available; (iv) Schools are > 5 km from a school in an adjoining clusters/zone that has been enrolled in the study (in that case, we will use simple random selection to determine which school gets excluded); (v) Government-run schools. In case of multiple eligible schools per Zone (cluster), one school that meets the eligibility criteria will be randomly selected. Stratification will be done based on the number of learners in the 11-16 age group per school, wherein all clusters will be ranked from high to low and each pair from top to bottom of the list will be randomly allocated. Randomization will be performed by an independent statistician using a random number generator in Stata statistical software. Randomization will be performed before conducting baselines because this is necessary for logistics (planning of venues, transport).

2.8.2. Random selection of participants

Next, we will employ a stratified block random selection approach to recruit children into the study. We will divide the total sample of children (see below) equally over all eligible schools across the clusters (i.e. Total sample/ Total eligible schools across zones = Sample per school), to make sure there is an equal distribution across schools. That number of children (n=252 per school) will be randomly selected from the school's pupil lists, stratified for gender (1:1), only including eligible children in that random selection process. Eligibility criteria for individual participant are: (i) Residents of the program area; (ii) Age 11-16 at the time of baseline; (iii) (Kinyabwisha, Speaking primary language Congolese Kiswahili, Runyankole, Runyoro/Rutooro). Random selection will be performed by an independent statistician using a random number generator in Stata statistical software. Siblings will not be excluded.

2.8.3. Sample size calculation

[figure not shown]
This cRCT was designed to have at least 80% power to detect a moderate effect size of Cohen's d = 0.30 for the primary outcome (MMAPP) at the primary time point (endline). Assumptions were the following: intra-cluster correlation coefficient (ICC) due to clustering by zone/school of 0.04 (based on population level data from two systematic reviews on ICCs [Shackleton et al, 2016; Parker et al, 2023]), 2-tailed 5% significance level, resulting in an estimation of 18 clusters (9 per arm) and n=176 children per cluster. Adjusted for a loss to follow-up rate of 30% makes the total sample size n=4536 (across study arms) – translating to n=252 per school. The LTFU

rate is a somewhat conservative estimate, as we will attempt to follow-up all participants enrolled at baseline, even if they leave school. We will not adjust for household level clustering (as siblings are included) in the analyses, and therefore this has not been included in the sample size calculations.

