2.10. Analyses

2.10.1. Effectiveness analyses [RQ1]

Primary comparison: (i) Baseline-to-endline comparison on MMAPP total score and (ii) baseline-to-endline comparison on Stirling total score.

Secondary comparisons: (iii) Baseline-to-endline comparison on all secondary, indirect and mediating outcomes; (iv) Baseline-to-midline on all outcomes; (v) Midline-to-endline on all outcomes. The analysis will follow an intention-to-treat approach, analyzing all participants based on their random assignment to the trial arms. Preliminary analysis will compare baseline characteristics to assess successful randomization across trial arms. Multilevel mixed-effect linear or logistic regression models (depending on outcome) will be employed for all primary, secondary, mediation, and indirect outcomes, treating the intervention group as a fixed effect. These models will account for the hierarchical structure of the data, with children nested within schools. Demographic variables and baseline outcome measures will be included as covariates. Additionally, (vi) we will evaluate mediation effects of social connectedness, hope and family functioning; (vii) Separate models will estimate differences between trial arms at the 6-month midline and 12-month endline, with distinct sub-group analyses for boys and girls; (viii) sensitivity analyses will be conducted wherein siblings are excluded; and (ix) analyses of the relative contribution of interventions or combination of interventions to change in the primary outcomes. A detailed Statistical Analyses Plan (SAP) will be developed and will be made publicly available before the end of the last data collection has been completed.

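### Ruling out household adjustment in all analyses makes intervals modestly too narrow for the BeThere contribution and the family-functioning-to-outcome path; the randomised arm comparisons are not materially affected

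*Protocol*

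**What the plan says.** Section 2.8.2 draws 252 children per school from the pupil lists and states "Siblings will not be excluded". Section 2.8.3 states "We will not adjust for household level clustering (as siblings are included) in the analyses", and continues "therefore this has not been included in the sample size calculations". Section 2.10.1 uses multilevel models for primary, secondary, mediation and indirect outcomes: "These models will account for the hierarchical structure of the data, with children nested within schools". No household level appears.

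The same section plans three further analyses that bear on this point:
- item (vi): "we will evaluate mediation effects of social connectedness, hope and family functioning";
- item (viii): "sensitivity analyses will be conducted wherein siblings are excluded";
- item (ix): "analyses of the relative contribution of interventions or combination of interventions to change in the primary outcomes".

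BeThere is delivered to caregivers (section 2.3.1) and reaches the sampled children indirectly through them (section 2.8.4). Family functioning is measured by SCORE-15, listed among the child-reported mediators in Table 2; its items describe the family.

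**The concern.** The sentence in section 2.8.3 is a decision, not a detail left open for the statistical analysis plan, and it covers the analyses without exception. Having siblings in the sample is a reason to consider household dependence, not a reason to set it aside.

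Whether ignoring it matters depends on the level at which the compared factor varies. Arm varies between zones. Receipt of BeThere varies between households within a school, and siblings with the same caregiver share it. Family functioning is each child's own report, but siblings report on the same family. For these two factors a model of children within schools treats siblings as independent information on something they share, and the standard error comes out too small. At stake is the stated precision of part of RQ2: which components, and which mediator, are credited with the effect. The only sibling-related check, item (viii), changes the analysed sample and corrects no standard error in the main analysis.

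**Working it through.** **1. The plan's own figure.** Inputs from section 2.8.3: d = 0.30, school ICC 0.04, two-sided 5%, 9 clusters per arm, 176 children per cluster, 30% loss.
- Design effect: 1 + (176 - 1) x 0.04 = 8.0.
- Effective n per arm: 9 x 176 / 8.0 = 198.
- Noncentrality: 0.30 / sqrt(2/198) = 2.985. Noncentral t with 18 - 2 = 16 df: power 0.800.
- Recruitment: 176 / 0.70 = 251.4, so 252 per school; 252 x 18 = 4536.

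The stated sample size reproduces.

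**2. Assumed inputs.** The protocol gives no sibling share and no household ICC.
- q, the proportion of eligible pupils with one eligible sibling in the same school: assumed 0.3-0.5.
- N, eligible pupils per school: section 2.8.1 requires more than 300, so the smallest is 301; 1,000 is assumed at the upper end.
- s, the share of analysed children with an analysed sibling. If siblings are lost independently, 176 of N are analysed and s = q x 175/(N - 1). Low: 0.3 x 175/999 = 0.053. High: 0.5 x 175/300 = 0.292. So s is about 5-29%.
- Household ICC (rho) for child outcomes: assumed 0.3-0.5.

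**3. Arm comparison.** With sibling pairs, the design effect becomes 8.0 + s x rho.

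| s | rho | design effect | power |
|---|---|---|---|
| 0 | - | 8.00 | 0.800 |
| 0.05 | 0.3 | 8.02 | 0.799 |
| 0.29 | 0.5 | 8.15 | 0.793 |
| 0.40 | 0.6 | 8.24 | 0.788 |
| 0.60 | 0.96 | 8.58 | 0.772 |

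The last row approximates one caregiver's score entered twice in a sample with very many siblings. Validity was checked by simulation under no effect (4,000 runs per setting, 18 schools of 176, household ignored, s 0.2-0.6, rho 0.3-0.96). Type I error of the arm test was 0.045-0.054, and model SE over true SE was 1.01-1.02. Intervals for arm effects are not too narrow, even at the caregiver-like extreme.

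**4. Household-level contrast within schools.** When siblings share the exposure fully, as with BeThere receipt, the variance is inflated by 1 + s x rho, and the naive SE is 1/sqrt(1 + s x rho) of the true one. The actual level of a 5% test is 2 x [1 - Phi(1.96 x SE ratio)].

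| s | rho | inflation | SE too small by | actual level |
|---|---|---|---|---|
| 0.05 | 0.3 | 1.015 | 0.7% | 5.2% |
| 0.05 | 0.5 | 1.025 | 1.2% | 5.3% |
| 0.29 | 0.3 | 1.087 | 4.1% | 6.0% |
| 0.29 | 0.5 | 1.145 | 6.5% | 6.7% |

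If siblings always left the study together, the share at the high end would be 0.5 x 251/300 = 0.42. With rho = 0.5 the inflation is 1.21, the SE is 9% too small and the level is 7.5%. A simulation of 6,000 runs at that setting gave 7.6%.

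**5. Family functioning.** Siblings' reports agree only in part, so the inflation is 1 + s x rho(mediator) x rho(outcome). With 0.5 for both and s = 0.29 it is 1 + 0.29 x 0.25 = 1.07, and the SE is about 3% too small. The table in step 4 is therefore an upper bound for this path.

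**The case against.** The case for leaving the plan alone is strong on most fronts, and several wider readings should be set aside.

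- **Primary and caregiver outcomes.** A reader might infer that these intervals are also too narrow. They are compared by arm, arm is allocated by zone, and step 3 shows the test holds its level. Item (ix) concerns the primary outcomes, which are adolescent-reported, so caregiver outcomes are not analysed against a household-level exposure there.
- **All three mediators.** A reader might treat them all as household quantities. Hope and social connectedness are individual scales; only family functioning has a clear household component. Its arm-to-mediator path is protected by the cluster allocation, which leaves the mediator-to-outcome path.
- **The bracket in the sentence.** It can be read as explaining why household clustering exists rather than as the reason for ignoring it. On that reading the sentence gives no reason at all, and it still rules out adjustment.
- **Item (viii).** A reader might infer that every child with a sampled sibling is dropped, which would change the population studied. The text does not say so; keeping one child per household fits it equally well. What stands is that the item is ambiguous.
- **Priority.** The affected analyses are non-randomised, and RQ2 objective (i) aims only to improve understanding. BeThere is open to any caregiver, so self-selection limits item (ix) more than an error of a few per cent in the SE. That is true and keeps the point small, but it does not make the intervals correct.

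The promised statistical analysis plan could settle the model for item (ix). As written, though, the protocol sentence points it to the wrong choice.

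**Conclusion.** The point holds in a narrow form. The blanket exclusion of household adjustment leaves the randomised comparisons sound: primary outcomes, caregiver outcomes by arm and the arm-to-mediator path. Power falls by less than one percentage point under the assumed inputs (0.800 to 0.793 at worst), so the sample size need not change.

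For the BeThere contribution in item (ix), and to a lesser degree the family-functioning-to-outcome path, standard errors are about 1-7% too small and a nominal 5% test runs at about 5-7%. This rests on an assumed sibling share of 5-29% after independent loss, sibling pairs rather than larger sibships, and a household ICC of 0.3-0.5. None of these is in the protocol; more siblings, or siblings lost together, would raise the figures. Severity: minor.

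**What to change.** - **Section 2.8.3:** limit the sentence to the sample size and the comparison by arm, and give the correct reason: with allocation by zone, household variance is absorbed at school level.
- **Section 2.10.1, item (ix) and the mediation models:** use household-robust standard errors or a household random intercept within school. No household term is needed for the other outcomes.
- **Section 2.10.1, item (viii):** define it as keeping one randomly chosen child per household, so that no household is lost.

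The cost is a few lines of wording and a link between children of the same household, which the caregiver household roster in Table 2 should make possible. If siblings turn out to be few, the household variance may be poorly estimated; the robust standard errors should then be used.

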2.8.4. Sample description

Important for this study, as described above, the randomly selected sample of children may or may not receive services following baseline assessments, similarly peers of the recruited children (children in the same school) may or may not receive services. This means that the impact of the mental health care system on recruited children may be direct (receiving TeamUp and/or EASE), and/or it may be indirect through their caregivers (receiving BeThere), and/or it may be indirect through their peers (receiving TeamUp or EASE, or their caregivers receiving BeThere). Furthermore, this service provision might happen in the first [approximate] 6 months or the second [approximate] 6 months. This is summarized in Figure 5.

Figure 5. Study samples

2.9.Procedures

2.9.1. Data collection – quantitative outcomes

The administration of the instruments will be conducted by 60 research assistants employed by the War Child Alliance. All research assistants will be specifically trained to conduct quantitative assessments. Research assistants receive a 5-day training course that includes research ethics, practice administration of surveys through interviews, communication skills, research procedures etc. Data collection for children will take place in a closed venue (e.g. classroom) or private room either on school premises or in their homes (only for school dropouts at follow-up), following War Childs child safeguarding procedures. Following the training, research staff will have 2 weeks of practice assessments and interview role plays until the start of the trial. Research assistants will also be trained in the Adverse Events Reporting Mechanism, which guides the process of reporting and supporting/referral in case of any adverse events (see further details below). First, the interview-administered instruments will take approximately 60-90 minutes to complete. The instruments will be administered individually to each participant, though participants may be asked to self-administer several key sensitive items to avoid social desirability. Such items will be identified from the adaptation work currently underway and for which we have ethics approval from MAKSHSREC [29/08/24] The administration of the instruments for the primary caregiver will take place either on school premises, or in the participants' homes, and should last approximately 30 minutes. Data collection with adolescents and caregivers will be done in person. Data will be collected electronically using Android tablets linked to the ODK platform (https://getodk.org/). All data collection will be conducted in Kinyabwisha, Congolese Kiswahili, Runyankole, Runyoro/Rutooro, which are the most spoken languages in the study sample. Each study participant will receive a small receive a gift for compensation (e.g. pens for adolescents and sugar for caregivers) for each assessment. Furthermore, refreshments (i.e. something to drink, and a snack) will be provided during all assessment sessions, for adolescents and caregivers.

